3.1 General Design

We will conduct a single-arm, pre-and post-design clinical trial. Outcome measures include: 1) feasibility (barriers to implementation, safety, and satisfaction) of the proposed intervention [Primary aim]; and 2) preliminary efficacy (lymphedema progression, symptom burden, and functional status) of the proposed intervention [Secondary aim]. Study assessments will take place at baseline, immediately after end of the intervention, and 4-week post-intervention.

CONFIDENTIAL

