4.5 Total Number of Subjects and Sites

Total number of subjects: 25

Single-site study: Subjects will be enrolled at Penn only.

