6.3 Subject Withdrawal

Subjects may withdraw from the study at any time without impact to their care. They may be discontinued from the study at the discretion of PI [name], due to lost follow-up or adverse events. Subjects may also be withdrawn by PI [name] from the study given safety consideration.

CONFIDENTIAL

7 Statistical Plan and Statistical Analysis

While this study is a preliminary study of efficacy and effect sizes, a maximum alpha level of 0.05 will be used for the statistical tests.

Statistical analysis for primary aim (feasibility of the intervention): Descriptive statistical and graphical methods will summarize the rates of participation (recruited vs. consented), log data (e.g., sessions completed), completion of assessments throughout the study, adverse events (safety) and satisfaction data within both groups. It is expected that $\geq 80\%$ of participants will complete the study activities, and $\geq 80\%$ will report acceptable levels of satisfaction with the interventions, thereby demonstrating feasibility of the interventions proposed in this research.

For the secondary objective, change from baseline value will be computed for each outcome variable at each follow-up timepoint. The analysis of changes over time relies on mixed-effects modeling, which accounts for correlation among subjects' repeated measures using a compound symmetry covariance matrix. Results will be reported as model-based mean change \pm standard error.

8 Safety and Adverse Events

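### Modelling unadjusted change scores would leave out participants with no follow-up value, and the mean change can be biased if both dropout and change relate to baseline

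*Combined protocol and SAP*

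**What the plan says.** Section 7 (Statistical Plan and Statistical Analysis) sets out the secondary analysis in three steps. First, "change from baseline value will be computed for each outcome variable at each follow-up timepoint". Then: "The analysis of changes over time relies on mixed-effects modeling, which accounts for correlation among subjects' repeated measures using a compound symmetry covariance matrix". Finally: "Results will be reported as model-based mean change", with its standard error. The response variable is not named. No baseline covariate, analysis set, missing-data assumption or sensitivity analysis is given.

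Section 3.1 fixes three assessments: "Study assessments will take place at baseline, immediately after end of the intervention, and 4-week post-intervention". Sections 6.2.1 to 6.2.3 collect the same lymphedema, symptom and neck-motion measures at each. Section 4.5 gives "Total number of subjects: 25". Section 6.3 foresees withdrawal, loss to follow-up and discontinuation. The feasibility criterion in Section 7 expects that at least 80% "of participants will complete the study activities".

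**The concern.** A change score exists only where both a baseline and a follow-up value exist. If change scores are the response, a participant seen only at baseline supplies no row, and the baseline value is discarded. A participant with one of the two follow-up visits still contributes.

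If those who leave differ from the rest at baseline, the remaining participants' mean baseline is shifted. Where change also depends on baseline, as it usually does through regression towards the mean, part of that shift enters the reported mean change. A mixed model normally protects against dropout that depends on observed values. That protection is lost when the predictor of dropout, the baseline, is in the model neither as a response nor as a covariate.

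The trial has one arm, so no comparison group can cancel the bias. Section 7 presents the work as a preliminary study of effect sizes, and Section 13 says that the data will help to design a larger trial.

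**Working it through.** The plan gives no SD, correlation or power calculation for these outcomes, so there is no figure of its own to reproduce.

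**From the documents:** 25 participants; at least 80% expected to complete, so 0.20 × 25 = 5 could fail to complete with feasibility still declared.

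**Assumed, because the documents do not say:** normally distributed outcomes; all 20% lack both follow-ups; baseline to follow-up correlation ρ of 0.3, 0.5 or 0.7; logistic dropout on baseline with odds changing 2-, 3- or 5-fold per SD. All results are in baseline SDs.

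**Step 1: formula.**
- Bias in mean change = (slope of change on baseline) × (shift in the completers' mean baseline).
- Slope = ρ × (follow-up SD / baseline SD) − 1, which is ρ − 1 when the SDs are equal.
- SE with 20 completers = √(2(1 − ρ)/20).

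**Step 2: shift.** With 20% dropout, more likely at higher baseline, numerical integration gives a completers' shift of −0.130, −0.186 and −0.235 SD for odds of 2-, 3- and 5-fold.

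**Step 3: bias, equal SDs.**

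| ρ | Slope | Bias, 2-fold | Bias, 3-fold | Bias, 5-fold | SE | Bias/SE |
|---|---|---|---|---|---|---|
| 0.3 | −0.7 | 0.091 | 0.130 | 0.164 | 0.265 | 0.34 to 0.62 |
| 0.5 | −0.5 | 0.065 | 0.093 | 0.117 | 0.224 | 0.29 to 0.52 |
| 0.7 | −0.3 | 0.039 | 0.056 | 0.070 | 0.173 | 0.23 to 0.40 |

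Simulated trials of 25 agree: 0.04 to 0.17 SD across the table. At ρ = 0.5 a 5% test of no change rejects 5.7% to 7.8% of the time when nothing has changed. If higher scores are worse and severe participants leave, improvement is understated. If mild participants leave, it is overstated.

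**Step 4: limits.**
- Extreme case, the most severe 20% all leave: the shift is −0.280/0.8 = −0.350, and the bias is 0.245, 0.175 and 0.105 SD for ρ = 0.3, 0.5 and 0.7. Each is still below its SE.
- 10% with no follow-up value: 0.03 to 0.06 SD at ρ = 0.5.
- Dropout unrelated to baseline: simulated bias within 0.001 SD of zero.
- Change unrelated to baseline (slope 0), same dropout: −0.001 to −0.002 SD in simulation.

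**Step 5: does modelling the measured values remove the bias?** This takes 20% dropout with 5-fold odds. Compound symmetry (CS) and unstructured (UN) are both fitted to all three visits.

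| True pattern | Change scores | CS | UN |
|---|---|---|---|
| Equal SDs, all correlations 0.5 | 0.12 | about 0 | about 0 |
| Correlation 0.5 with baseline, 0.8 between follow-ups | 0.12 | about 0.03 | about 0 |
| Correlation 0.3 with baseline, 0.8 between follow-ups | 0.16 to 0.17 | about 0.05 | about 0 |
| Follow-up SD 1.3 × baseline, correlations 0.7 and 0.85 | 0.02 | about −0.045 | about 0 |

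In the last row the slope is 0.7 × 1.3 − 1 = −0.09, and −0.09 × −0.235 = 0.021, as tabulated. The unstructured fit left 0.006 SD or less in every case. Compound symmetry on the measured values did not, and in the last row it was worse than change scores.

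**The case against.** The strongest reply is that Section 7 never names the response. A mixed model on the measured values at three visits, reporting change as a visit contrast, also fits wording about repeated measures and a model-based mean change. That stands as an ambiguity. However, a plan that first computes change at each follow-up and then says "The analysis of changes over time relies on mixed-effects modeling" reads most naturally as modelling those changes; a measured-value model would not need them computed. The two readings treat baseline-only participants differently, and nothing in the plan settles the choice before the data are seen.

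Three stronger readings are tempting, and the documents do not support them.
- A reader might infer bias whenever dropout depends on baseline severity. Change must depend on baseline too, and Step 4 shows no bias when it does not.
- A reader might infer that the model only compares the two follow-up visits and so never tests change from baseline. With change as the response, each visit's model-based mean is itself the change from baseline, and its standard error gives the test against zero. The plan reports exactly that quantity.
- A reader might take the 80% criterion to mean that 5 of 25 will have no follow-up. It concerns study activities, which may include the 12 sessions. Someone who misses sessions, or only the last visit, can still have a change score, so 20% is an upper-end input.

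It is also fair to say that feasibility is the primary aim, and that efficacy is preliminary with no success threshold.

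**Conclusion.** The point holds as a conditional one. On the most natural reading, participants without any follow-up value are left out, and the mean change can be biased when both dropout and change relate to baseline. Under the stated assumptions the bias is about 0.04 to 0.17 SD, roughly a quarter to three-fifths of a standard error.

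That it stays below one standard error depends on the 20% ceiling. With 30% lost, all of them the most severe, it would not: 0.348 against 0.283 SD at ρ = 0.3. The correlation, the dropout pattern and normality are assumptions; the documents neither support nor exclude them.

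This is a moderate weakness in a secondary analysis and does not touch the feasibility aim. It is worth correcting because a better analysis uses data already being collected.

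**What to change.** In Section 7:
- Fit the mixed model to the measured values at baseline, end of intervention and 4 weeks post-intervention, with visit as a three-level factor and every participant with a baseline included.
- Replace compound symmetry with an unstructured covariance. Over three visits this has 6 parameters (3 variances and 3 covariances) instead of 2. Changing the response while keeping compound symmetry is not enough, as Step 5 shows.
- Report change as the contrasts Visit 2 minus baseline and Visit 3 minus baseline, with standard errors.
- State that the analysis assumes data missing at random given the observed values, and report how many participants have no follow-up value.
- Keep the change-score analysis as a sensitivity analysis.

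The cost is a few sentences, with no new data and no new participants. The downside is a somewhat larger standard error when dropout depends strongly on baseline: for example 0.229 against 0.220 SD, and 0.229/0.220 = 1.04, about 4%. If the measured-value model was already intended, the text records that and only the covariance changes.

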3.2.2 Secondary Study Endpoints

The secondary study endpoint will be the potential efficacy of LLLT in HNC patients, including lymphedema progression, symptom burden, and functional status.

4 Study Population and Duration of Participation

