6.2 Study Intervention Phase

6.2.1 Visit 1: Baseline Visit

The following procedures and data collection will take place at study visit 1.

- Demographic Form
- Physical Exam for completing HN-LEF Grading Criteria
- Digital photographs of face and neck
- Modified Patterson Scale
- Symptom burden assessments (LSIDS-H&N and NDI)
- Functional status (neck range of motion)

In addition, the following variables will be abstracted from the medical chart with participants' permission.

- HNC Disease and treatment information (HNC Clinical Form)
- Lymphedema and fibrosis diagnosis and treatment information (LEF Treatment Form)

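### Secondary outcomes, including the HN-LEF grading, are reported only as mean change, so the plan never shows how many participants' lymphedema progressed

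*Combined protocol and SAP*

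**What the plan says.** Section 3.2.2 describes the secondary endpoint as potential efficacy, "including lymphedema progression, symptom burden, and functional status". Sections 6.2.1 to 6.2.3 list the same assessments at baseline, at the end of the intervention and four weeks later. The first is "Physical Exam for completing HN-LEF Grading Criteria"; photographs, the Modified Patterson Scale, two symptom questionnaires (LSIDS-H&N and NDI) and neck range of motion follow. The lists label the questionnaires as symptom burden and range of motion as functional status. They give no such label to HN-LEF, the photographs or the Modified Patterson Scale.

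Section 7 sets out the secondary analysis in three sentences. First: "For the secondary objective, change from baseline value will be computed for each outcome variable at each follow-up timepoint". Second: "The analysis of changes over time relies on mixed-effects modeling, which accounts for correlation among subjects' repeated measures using a compound symmetry covariance matrix". Third: "Results will be reported as model-based mean change" with its standard error. No other summary of a secondary outcome is planned. The documents do not define progression, and they plan no count of participants who worsened, no shift table and no ordinal method.

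The primary aim is handled differently: "Descriptive statistical and graphical methods will summarize the rates of participation (recruited vs. consented), log data (e.g., sessions completed", along with assessment completion, adverse events and satisfaction.

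**The concern.** Progression invites the question of how many participants got worse. A mean change answers another question: where the group moved on balance. For a graded outcome the mean has two weaknesses. It counts every one-grade step as the same size, wherever on the scale it occurs. It also nets improvement in some participants against worsening in others.

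The protocol gives its own reasons to want the split. Sections 1 and 1.1 describe lymphedema as chronic and prone to worsen. Section 11.1 uses worsening lymphedema as its example of a physical risk and says there are no safety data in this population. Section 13 says the results will inform the design of a larger trial. The proportions worsened, stable and improved are useful for that design and cannot be recovered from a mean and its standard error.

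**Working it through.** **The plan's own figure.** There is none to reproduce. The documents give no power calculation, effect size, standard deviation or expected progression rate.

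**Inputs from the documents.** Section 4.5: "Total number of subjects: 25". There are three assessments per participant (Sections 6.2.1 to 6.2.3), and the planned summary is mean change with its standard error (Section 7).

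**Assumed inputs.** All 25 are evaluable, 5 worsen by one grade (+1), 5 improve by one (−1) and 15 do not change (0). This split is chosen to show the mechanism. It is not a forecast.

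**Mean-change summary.**
- Mean = [5(+1) + 5(−1) + 15(0)] / 25 = 0.00.
- SD = √[Σd² / (n − 1)] = √(10/24) = 0.645.
- Simple SE = 0.645 / √25 = 0.129, giving a 95% interval of about ±0.27 (t, 24 df).

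**Share who progressed.**
- 5/25 = 20%.
- Exact (Clopper-Pearson) 95% limits: the 2.5% point of Beta(5, 21) = 0.068 and the 97.5% point of Beta(6, 20) = 0.407.

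**Check with a mixed model.** A random-intercept model, which implies compound symmetry, was fitted to a constructed set of 25 participants and three visits. The first follow-up used the split above. At the second, one further participant was up and one down. Estimated change was 0.00 at both follow-ups, with SE 0.115. The SE differs from 0.129 because the model pools residual variance over visits.

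**Other splits.**

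| n | Split | Mean (simple SE) | Progressed (exact 95% CI) |
|---|---|---|---|
| 25 | 5 up, 5 down, 15 unchanged | 0.00 (0.129) | 20% (6.8% to 40.7%) |
| 25 | 10 up, 10 down, 5 unchanged | 0.00 (0.183) | 40% (21.1% to 61.3%) |
| 20 (assumed evaluable) | 4 up, 4 down, 12 unchanged | 0.00 (0.145) | 20% (5.7% to 43.7%) |

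The offset need not be one for one: 4 up by one grade and 2 down by two gives [4(1) + 2(−2)] / 25 = 0, with 4/25 = 16% progressing. But there must be some improvement to offset. With 5 worse and none better the mean is 5/25 = 0.20. Even that value does not fix the count, because 10 worse and 5 better also gives (10 − 5)/25 = 0.20, with 40% progressing instead of 20%.

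**Would a rank test help?** In the 5-up, 5-down example all ten non-zero differences have size 1 and share the average rank 5.5. The signed-rank sums are 5 × 5.5 = 27.5 on each side, so the test also shows no net shift. Only the counts show the split.

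The equal-steps problem cannot be sized, because the documents do not give the number of HN-LEF grades or how they are scored.

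**The case against.** The strongest reply is that average change is a reasonable target for preliminary efficacy. Section 2 states the goal as the effect on swelling and fibrotic changes, and all participants have lymphedema at entry (Section 4.1). Equating progression with the number who worsen is a reading, since the protocol does not define the term. Any mean nets gains against losses, so that argument alone would also count against means of questionnaire scores and range of motion. The example's symmetry was chosen to give zero. The investigators could also add a table later from the same data. All of this stands, and it limits the weight of the point. It does not change the fact that the only summary planned for a graded outcome under an endpoint called progression leaves out the number who progressed.

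Four stronger readings are tempting, and the documents do not support them.

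- **That every outcome in the trial is reduced to a mean.** Section 7 confines this rule to the secondary objective; feasibility outcomes, including adverse events, are summarised descriptively.
- **That a linear model is specified.** Section 7 names only mixed-effects modelling. Linear is the natural inference from mean change with compound symmetry, but it is not stated.
- **That HN-LEF is the stated measure of progression.** It is listed beside photographs, which Section 8.5.1 says are scored, and the Modified Patterson Scale. None of the three is assigned to an endpoint. That HN-LEF yields a grade is inferred from its name.
- **That harm would be hidden.** Section 8.2 seeks adverse events at each contact, by questioning and where appropriate by examination. Sections 8.1 and 8.2 name an abrupt rise in swelling as a sign to act on. Section 8.4 halts recruitment and study activities after any event that may have caused harm. In a single-arm study of a condition that tends to worsen, 5 of 25 worsening would not in itself be a harm signal. The remaining gap is narrow: nothing says that a gradual one-grade worsening found at a scheduled examination is recorded as an adverse event.

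**Conclusion.** The point holds in limited form. For the secondary objective the plan reports only mean change and its standard error, HN-LEF grading included, so it never yields the number of participants who progressed. In the illustration a mean of 0.00 (simple SE 0.13) sits beside a progression share of 20% (exact 95% CI 7% to 41%). Across the zero-mean splits shown, the share runs from 16% to 40%.

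This rests on two inferences, that HN-LEF yields a grade and that it contributes to the progression endpoint, and on an assumed split with offsetting improvement. The endpoint is secondary and the study is a pilot, so this is a cheap improvement to the analysis text and does not undermine the design.

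**What to change.** In Section 7, for HN-LEF and any other secondary outcome recorded as a grade:

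- Make the main summary at each follow-up the number and percentage worsened, unchanged and improved, each with an exact 95% confidence interval.
- Add a table of baseline grade by follow-up grade.
- State that worsening by at least one grade counts as progression for this analysis.
- Treat any ordinal model or rank test as optional. It tests net shift only and does not replace the counts.

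Keep the mixed model and mean change for questionnaire scores and neck range of motion. If HN-LEF in fact gives a continuous score, say so and define progression on that score.

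The cost is a few lines of text and one extra table, with no new data, visits or participants. The downside is wide intervals at n = 25, about 34 percentage points in the example (40.7 − 6.8 = 33.9).

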8.1 Safety Monitoring

The following strategies will be in place to monitor safety of participants during the course of the study.

During the course of this study, study staff will observe for any adverse side effects or events when interacting with participants and be trained to report these to the PI's immediately. Common Terminology Criteria for Adverse Events (CTCAE version 4.03) will be used to document adverse events of the trial. All the staff members who are involved in this study will be trained how to use CTCAE version 4.03.

In addition, participants in this study will be screened against the inclusion and exclusion criteria. Participants will be educated regarding signs and symptoms related to adverse events (e.g., sudden increase in swelling) requiring urgent or emergent medical care.

8.2 Recording of Adverse Events

Each contact with the subject, the trained staff will seek information on adverse events by specific questioning and, as appropriate, by examination. Information on all adverse events will be recorded immediately in the source document, and also in the appropriate adverse event module of the case report form (CRF). All clearly related signs, symptoms, and abnormal diagnostic procedures results should be recorded in the source document.

All adverse events occurring during the study period will be recorded. The clinical course of each event will be followed until resolution, stabilization, or until it has been determined that the study intervention or participation is not the cause. Serious adverse events that are still ongoing at the end of the study period will be followed up to determine the final outcome. Any serious adverse event that occurs after the study period and is considered to be possibly related to the study intervention or study participation will be recorded and reported immediately.

All adverse events will be reviewed by Drs. [name] and [name], any contributing factors will be reviewed, and strategies to prevent further complications will be developed and implemented. [name] will meet with study staff monthly to evaluate any other safety concerns. Adverse events will be reported to the Penn IRB within the window required by the IRB. If study staff identify the following unanticipated problems related to the research (e.g., infection in the treated area, sudden increase in swelling), which occur during the study, Drs. [name], [name], and study lymphedema therapists will be notified immediately. Patients will be referred and receive appropriate and timely therapy. Drs. [name] and [name] will determine if participants with adverse events or any unexpected issues will remain on the study based on safety consideration. Drs. [name] and [name] as well as the study lymphedema therapist will evaluate the relationship of each adverse event to the study procedures. PI [name] and Co-I [name] will be responsible for making the determination of the relationship

CONFIDENTIAL

of the adverse event to the study procedures (e.g., definitely related, probably related, possible related, unlikely or unrelated).

8.3 Reporting of Adverse Events, Adverse Device Effects and Unanticipated Problems to Penn IRB and ACC

PI [name] and the study team will conform to the adverse event reporting timelines and formats, per the Penn IRB reporting requirements and Abramson Cancer Center reporting guidelines.

The following information will be included at the time of the initial report:

- Study identifier
- Study site
- Subject number
- A description of the event
- Date of onset
- Current status
- Whether study intervention was discontinued
- The reason why the event is classified as adverse events
- Investigator assessment of the association between the event and study intervention

Additionally all other events (unanticipated problems, adverse reactions, unanticipated adverse device effects and subject complaints) will be recorded and reported with respect to Penn policies as described in the Penn Manual.

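### Participants removed from the study for an adverse event such as sudden swelling have no planned outcome assessment afterwards, so the secondary mean change can be biased towards benefit

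*Combined protocol and SAP*

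**What the plan says.** **Removal.** Section 6.3 says of participants: "They may be discontinued from the study at the discretion of PI", and gives the grounds as "due to lost follow-up or adverse events". Section 8.2 says the study doctors "will determine if participants with adverse events or any unexpected issues will remain on the study based on safety consideration". Both sections speak of the study, not of the laser.

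**Trigger.** Section 8.1 has participants taught about "signs and symptoms related to adverse events (e.g., sudden increase in swelling) requiring urgent or emergent medical care". Section 8.2 gives as examples of unanticipated problems "e.g., infection in the treated area, sudden increase in swelling" and adds: "Patients will be referred and receive appropriate and timely therapy".

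**Outcome.** Section 3.2.2 defines the secondary endpoint as potential efficacy, "including lymphedema progression, symptom burden, and functional status". Sections 3.1 and 6.2.1 to 6.2.3 place the efficacy measures at baseline, end of the six-week intervention (Visit 2) and four weeks later (Visit 3), with none in between.

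**Analysis.** Under Section 7, "change from baseline value will be computed for each outcome variable at each follow-up timepoint", and changes over time are analysed with a compound-symmetry mixed model. Section 7 states no analysis population, missing-data assumption or sensitivity analysis. No section says whether a removed participant is still assessed.

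**The concern.** A sign that can lead to removal overlaps with something the trial is measuring. If a participant's swelling worsens during the six treatment weeks and the doctors take that person off the study, the worsening never enters the efficacy data, because the next scheduled measurement is Visit 2. Those left in the analysis are then, on average, the ones who did better.

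There is no control arm in which similar losses might offset this, so any selective loss passes straight into the reported mean change. Section 13 says the results will inform the design of a larger efficacy trial, and an optimistic estimate would carry over into it.

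**Working it through.** **Inputs from the protocol.** N = 25, single arm (Sections 3.1 and 4.5). Maximum alpha 0.05, sidedness not stated (Section 7). Completion target at least 80%, so 0.80 x 25 = 20 completers, and up to 25 - 20 = 5 losses still meet it (Section 7). The documents give no effect size, SD, dropout rate or removal rate, so there is no planned figure to reproduce.

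**Assumptions, not from the protocol.** Changes are normal with SD 1 and true mean 0, higher meaning worse. Tests are two-sided at 0.05. Between 0 and 5 participants are removed.

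**Step 1: removal before Visit 2, analysis of observed change scores.** With the worst k removed, the analysed mean is the sum of the remaining changes divided by 25 - k. Simulation with 100,000 runs, followed by a one-sample t-test, gives:

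| Removed (k) | Shift towards benefit (SD) | Chance of a false significant benefit |
|---|---|---|
| 0 | 0.00 | 2.4% |
| 1 | 0.08 | 7% |
| 2 | 0.15 | 14% |
| 3 | 0.22 | 23% |
| 4 | 0.28 | 34% |
| 5 | 0.33 | 46% |

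For scale, the standard error of a mean of 25 changes with SD 1 is 1/√25 = 0.20 SD.

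**Step 2: removal only partly linked to the outcome.** Here removal follows a signal with correlation rho to the true change (20,000 runs per case).

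| rho | Shift, k = 1 | Shift, k = 3 | Shift, k = 5 | False benefit, k = 1 to 5 |
|---|---|---|---|---|
| 0 | 0.00 | 0.00 | 0.00 | about 2.4% |
| 0.3 | 0.03 | 0.06 | 0.10 | 3% to 6% |
| 0.5 | 0.04 | 0.11 | 0.17 | 4% to 12% |
| 0.7 | 0.06 | 0.15 | 0.24 | 5% to 21% |

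**Step 3: does the mixed model repair it?** Section 7 can be read as modelling change scores. A participant with no post-baseline value then contributes nothing, as in Step 1. The more favourable reading keeps baseline as one of the repeated measures. Estimation under compound symmetry, with within-person correlation taken as known at 0.5 or 0.7 and the k worst Visit 2 changes lost (1,500 runs), gives:

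- Removal before Visit 2: the Visit 2 change is still biased towards benefit, by 0.06 to 0.07 SD for k = 1 and 0.26 to 0.28 SD for k = 5. Baseline alone does not carry the information that led to removal.
- Removal between Visits 2 and 3, depending on the recorded Visit 2 value: no detectable bias (within about 0.01 SD), because the model uses Visit 2.
- Everyone still assessed: no bias beyond simulation error of about 0.01 SD.

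The gap is therefore confined to removals during the treatment weeks, and continued assessment closes it under these assumptions.

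**The case against.** The strongest reply is that none of this need happen. Removal is discretionary in both sections. In Section 8.2 sudden swelling leads to notification, referral and therapy, and staying on study is a separate safety decision. Sections 8.5.1 and 10.1 call adverse events highly unlikely, and Section 8.4 halts study activities for review after any one event that may have caused harm, so several unreviewed removals are hard to imagine. The primary endpoint is feasibility, and Section 7 already summarises adverse events and completion of assessments, so losses would be visible.

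Much of this stands, and it rules out some stronger readings that a reader might infer:

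- *That the estimate is biased, or that the protocol removes participants who progress.* No rule does so.
- *That anyone removed lacks both follow-up values.* A person removed after Visit 2 already has a Visit 2 change.
- *That the protocol equates stopping the laser with leaving the study.* Sections 6.3 and 8.2 are silent on stopping the laser alone, and Section 8.3 lists discontinuation of the intervention as its own reporting item.
- *That swelling is the efficacy outcome.* It belongs to one of three domains, and an acute episode, perhaps with infection, need not equal graded progression. Step 2 allows for this.
- *That benefit would be overstated twofold.* That needs an observed improvement of 0.30 SD and three removed participants who each worsen by 1.0 SD: (22 x -0.30 + 3 x 1.0)/25 = -0.144 SD. With 0.5 SD worsening it is -0.204 SD, a ratio of about 1.5. None of these inputs is in the documents.

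The reply does not dispose of the point. Sections 8.4 and 11.1 also say that no safety data exist in this population, so a low rate cannot be relied on. Reporting or reviewing a removal does not restore the missing measurement.

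**Conclusion.** The concern holds as a risk that the plan leaves unguarded, not as a demonstrated bias. Removal before Visit 2 for worsening can bias the secondary mean change towards benefit, and the planned model would not correct it. The sizes, from zero with no removals to about 0.33 SD if exactly the worst five are lost, rest on assumed normal changes, a true mean of zero and assumed removal counts. The upper end also needs removal to track the outcome perfectly; a correlation of 0.5 roughly halves the shift. Feasibility conclusions are not affected in the same way. The change is worth making because outcome values not collected during the trial cannot be recovered at analysis.

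**What to change.** **Sections 6.3 and 8.2.** Separate stopping the study laser from leaving the study. Ask participants who stop the laser, and who still agree, to attend the planned Visit 2 and Visit 3 assessments. The clinical decision on who stops, and each participant's right to withdraw, stay as they are.

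**Section 7.** Include all enrolled participants. Report the number removed, the timing and reasons, and any therapy given for swelling. Pre-specify a sensitivity analysis that assigns a worsened value, over a stated range, to participants removed for increased swelling who have no later assessment.

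Counting every such participant as progressed is not advised. Section 7 reports mean change and has no progression summary to hold that count, and the rule would misclassify acute or unrelated swelling.

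**Cost.** Some wording, and up to two already planned visits for a few participants. Values recorded after an event may reflect the therapy given for it, which is why that therapy should be reported. The mean change may come out less favourable.
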